- New diagnosis of major depressive disorder or dysthymic disorder at a primary care visit ("new" defined as no depression diagnosis, psychotherapy visit or filled antidepressant prescription in the prior year)
- Continuously enrolled in the participating health system for 365 days prior to the eligible diagnosis (to assure capture of prior diagnoses or treatments)
- PHQ-9 depression score of 10 or more within 14 days before to 7 days after the eligible diagnosis
- No filled prescription for any antidepressant medication OR psychotherapy visit attended within 30 days of the eligible diagnosis\*
- No recorded PHQ-9 depression score less than 5 since the eligible diagnosis
- At least 18 years of age or older

The KP Hawaii site will enroll only patients who self-identified (based on EHR data) as Asian or Native Hawaiian or Other Pacific Islander. The Henry Ford site will enroll only patients self-identified as African American or Hispanic.

Potential participants will be excluded because of:

- Diagnosis of schizophrenia or bipolar disorder in the prior 2 years
- Not registered to use EHR patient portal
- Previously requested to not be contacted for research

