#### **Pilot Trial Design**

Each week, the computable EHR phenotype described above will be used to identify patients meeting criteria for failure to initiate depression treatment during the prior week. All eligible participants will be randomly assigned either to continued usual care (i.e. no contact from study staff) or to an outreach intervention described above. Engagement in care and recorded clinical outcomes over the subsequent 60 days will be assessed using health system records.

**Intervention Assignment** - All eligible patients will be randomly assigned (1:1 ratio) to either continued usual care or attempted outreach using a masked table of computer-generated random assignments. Randomization will be stratified by study site and use a permuted block design, with randomly varying block sizes of 4, 6, 8, 10 and 12.

**12.3 \* Provide a brief description about the quality management plan for the selection of study participants and integrity of the data. Specify the verification or audit process to ensure data and/or participants meet the study inclusion criteria. Additionally, describe the mechanism to ensure that study data is well secured and accurately entered. (e.g. two staff verification process to ensure entry criteria are met prior to using data or including a participant; safety reports; Data Safety Monitoring Board and/or screening checklists.)**

- All staff will be training in HIPAA privacy rules, human subjects protections, authorization of access by CIHR/HFHS IT, password protection, encryption, physical security, and separation of identifiers from data
- We plan to archive the deidentified data at the end of the study for the federally-mandated retention period or at least seven years, whichever is later.
- A Data Use Agreement will be executed between all sites prior to the transfer of any data. Data exchanged between the sites will contain the minimal information necessary and will be in the form of a limited data set.
- Data will be stored on password-protected encrypted devices and servers.

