No identifying information will be linked to the audio-recordings of the focus groups interviews. Participants will not be asked to state their name for voice linking. Audio-recordings will be sent to a professional transcriptionist via secured transfer. Once the transcription is received the audio-file will be permanently destroyed. All data will be transferred from an encrypted computer, which is password protected, to a secured server during data collection. Identifiers will be removed from all data obtained in this study and identifiers will be destroyed following the completion of the study, prior to closure of the IRB protocol.

We will convene a Data and Safety Monitoring Board including:

- A clinician with expertise regarding psychotherapy for depression ([name], VA Pacific Islands Health Care Division)
- A clinician with expertise regarding medication treatment for clinician ([name], Harvard University)
- A statistician with expertise regarding effectiveness or pragmatic trials ([name], National Center for PTSD, Palo Alto)

DSMB members will not be affiliated with research centers or health systems participating in this study.

The DSMB will meet three times during the pilot trial portion of the project:

- One meeting prior to beginning enrollment to review all study procedures

- One meeting when approximately half of the planned sample has been enrolled to review enrollment progress, quality/fidelity of intervention delivery, and any adverse events identified by or reported to study staff
- One meeting when the full sample has been enrolled to review enrollment progress, quality/fidelity of intervention delivery, any adverse events identified by or reported to study staff, and quality/integrity of outcome data

The DSMB will have authority to:

- Require changes to study procedures
- Terminate enrollment because of inadequate progress
- Terminate delivery of interventions because of concern regarding effective or safe delivery

Given the sample size, the relatively short recruitment period, and the delay in availability of outcome data extracted from health system records; we do not propose any interim analyses of study outcomes. Interim analyses prior to completion of enrollment would not have adequate power to detect either significant benefit or significant harm from the outreach intervention

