#### **12.4 \* Provide a description of the Statistical Analysis Plan (including rationale for number of subjects recruited for the study and the statistical method(s) by which the data will be analyzed)**

Based on previous MHRN research, we presume that 10% of participants assigned to usual care will initiate treatment within 60 days of randomization (after not initiating treatment in the first 30 days after diagnosis) and that only 2% will disenroll from participating health systems (i.e. outcome data not available) within 60 days. A sample size of 200 per group across both sites will afford 90% power (chi-square statistic with 2-sided type 1 error of 5%) to detect an increase from 10% to 22% in those assigned to the outreach intervention. Within any specific racial or ethnic group, the anticipated sample size of approximately 50 per group would afford 80% power to detect an increase from 10% to 33% in those assigned to the outreach intervention. In other words, this pilot study will have adequate power to detect moderate to large increases in treatment initiation and will not have adequate power to examine effects on ultimate clinical outcomes (i.e., HEDIS response and remission rates).

The primary trial outcome will be initiation of formal depression treatment within 60 days of randomization, defined as either at least one filled prescription for any antidepressant medication or attending at least one individual psychotherapy visit. Two secondary outcomes (recording of depression remission or response) will be defined and assessed using NCQA/HEDIS Electronic Clinical Data Systems specifications for depression response and remission. Those specifications identify recorded response (i.e. 50% or greater decrease in PHQ-9 score from baseline) and remission (i.e. any recorded PHQ-9 score of less than 5) among all patients with new diagnoses and baseline PHQ9 scores of 10 or higher. Following HEDIS specifications, failure to record clinical outcome will be considered failure to achieve response or remission.

Descriptive analyses will examine baseline participant characteristics (age, sex, baseline PHQ-9 score, history of prior depression treatment) and examine uptake or acceptance of specific intervention activities, including:

- Proportion of intervention participants reading initial outreach messages
- Proportion responding to initial outreach and completing outreach assessment

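### Untreated status is checked to day 30 after diagnosis but not to randomisation, and the primary outcome does not require a first treatment, so a few continuing patients can be scored as initiators (small effect, cheap to correct)

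*Combined protocol and SAP*

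**What the plan says.** Section 12.2, eligibility list: one criterion is "No filled prescription for any antidepressant medication OR psychotherapy visit attended within 30 days of the eligible diagnosis". The list also requires no treatment in the year before diagnosis, so the gap concerns only the period after diagnosis. The next criterion, on PHQ-9 scores below 5, has no such end point: it runs from the diagnosis onward.

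Section 12.2, Pilot Trial Design: the code is run each week to "identify patients meeting criteria for failure to initiate depression treatment during the prior week". Section 22.1 then has patients found eligible by the algorithm randomised. Neither section describes a second check of treatment status at randomisation.

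Section 12.4: the primary outcome, within 60 days of randomisation, is "at least one filled prescription for any antidepressant medication or attending at least one individual psychotherapy visit". The 10% usual-care assumption is for patients who start "after not initiating treatment in the first 30 days after diagnosis". From it the plan derives its power statement: "A sample size of 200 per group across both sites will afford 90% power" "to detect an increase from 10% to 22% in those assigned to the outreach intervention".

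Section 12.2, Phase III: a chart review sheet helps outreach clinicians tailor messages. It also has a quality-assurance purpose, namely to confirm that the algorithm's information agrees with the current record.

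Section 12.3: one reason for having no interim analysis is "the delay in availability of outcome data extracted from health system records".

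**The concern.** The outcome is called initiation, and the 10% assumption describes new starts, but the operational definition counts any fill or individual visit in the window. The eligibility rule does not keep out a patient who starts between day 30 and randomisation. For that patient, a refill or second visit inside the 60 days meets the definition.

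Outreach cannot bring about a start that has already happened. Such patients are likely events in both arms. They raise both rates, shrink the difference slightly and add variance. The usual-care rate is also something the pilot passes on to the planned full-scale trial (sections 10.2 and 12.1). If it includes refills, it overstates how often untreated patients start.

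**Working it through.** **1. The plan's power.** Inputs from section 12.4: 10% against 22%, 200 per arm, two-sided 5% chi-square. With pooled variance under the null,

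power = Φ{[Δ√n − 1.96·√(2p̄(1−p̄))] / √(pC(1−pC) + pT(1−pT))}.

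Here p̄ = 0.16, Δ√n = 0.12 × √200 = 1.697, √(2 × 0.16 × 0.84) = 0.5185 and √(0.09 + 0.1716) = 0.5115. So (1.697 − 1.016)/0.5115 = 1.331, and power is 0.908. At 196 per arm, after the plan's 2% disenrolment, it is 0.903. The stated 90% reproduces.

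**2. Share already treated, from the gap alone.** Inputs: 10% per 60 days (section 12.4) and a weekly run (section 12.2). Assumptions: a constant daily rate, and randomisation on the day of the run, so that the gap after day 30 is 0 to 7 days with a mean of 3.5.

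- Mean gap: f = 1 − 0.90^(3.5/60) = 0.6%, or about 2 of 400.
- Longest gap: f = 1 − 0.90^(7/60) = 1.2%, or about 5 of 400.

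**3. Effect on rates and power.** Assume that 80% of already-treated patients refill or revisit within 60 days (the documents give no figure). Each arm's rate becomes p(1 − f) + 0.8f.

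| f | Usual care | Outreach | Power, 200 per arm | Power, 196 per arm |
|---|---|---|---|---|
| 0 | 10.0% | 22.0% | 0.908 | 0.903 |
| 0.6% | 10.4% | 22.4% | 0.900 | 0.894 |
| 1.2% | 10.8% | 22.7% | 0.891 | 0.884 |

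**4. If the eligibility extract also lagged.** The documents do not state this and give no length, so these rows are conditional on f. The formula is the same.

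| f (assumed) | Usual care | Outreach | Power, 200 per arm |
|---|---|---|---|
| 2% | 11.4% | 23.2% | 0.878 |
| 5% | 13.5% | 24.9% | 0.827 |
| 10% | 17.0% | 27.8% | 0.738 |

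If every already-treated patient scored as an event, instead of 80%, the three powers would be 0.872, 0.813 and 0.712.

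As a rough guide to what such values of f would take: section 11.1 gives 36% initiating by day 90. With 10% over days 31–90, that implies (0.36 − 0.10)/0.90 = 28.9% by day 30, a daily rate of −ln(0.711)/30 = 0.0114 if starts are evenly spread. The later daily rate is −ln(0.90)/60 = 0.00176. With a mean gap of 3.5 days, a 7-day lag hides 3.5 days before day 30, so f = 1 − exp(−(0.0114 + 0.00176) × 3.5) = 4.5%. A 14-day lag hides 10.5 days, so f = 1 − exp(−(0.0114 × 10.5 + 0.00176 × 3.5)) = 11.8%. Both are lower if starts cluster at diagnosis.

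**5. With a first-since-diagnosis outcome.** Already-treated patients stay in the denominator but cannot be events, so the rates are p(1 − f). Power at 200 per arm is 0.906 and 0.904 at f = 0.6% and 1.2%, and 0.902, 0.891 and 0.871 at 2%, 5% and 10%. Most of the loss is recovered even if some treated patients still enter.

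**The case against.** **The intended target is clear.** Section 12.4 names the outcome as initiation, and Pilot Trial Design refers to failure to initiate. The eligibility code might already handle this, and it is not in the documents. That is fair as to intent, but the written definition still counts a refill.

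**Chart review may catch these patients.** It does have a quality-assurance purpose. However, it is described for outreach clinicians, with no stated equivalent for usual care, no timing relative to randomisation and no rule for a patient found to be treated. It cannot be relied on to secure untreated status in both arms. Nor do the documents say that such patients would be dropped from the outreach arm: section 12.4 analyses everyone as assigned.

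**A reader might infer that the plan admits its eligibility records lag.** It does not. The delay in section 12.3 is stated for outcome data, as a reason for no interim analysis. Fills and visits serve both purposes, so a lag at eligibility is a reasonable inference, but it remains an inference. The powers of 0.83 and 0.74 depend on it and should not be quoted as the plan's expected power.

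**A reader might also infer a biased comparison.** The eligibility and outcome rules are the same in both arms, so randomisation balances the misclassification in expectation. The harm is dilution and an overstated initiation rate, not a false positive.

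**Conclusion.** The point holds, and it is small. As written, treatment started between day 30 and randomisation does not exclude a patient, and continuing that treatment is scored as initiation. On inputs the documents support, this is about 0.6% of those randomised and at most 1.2%. Usual care would read 10.4–10.8% instead of 10.0%, and power 0.900–0.891 instead of 0.908 at 200 per arm (0.894–0.884 instead of 0.903 at 196). That rests on a constant start rate, randomisation on the day of the weekly run, and 80% refilling or revisiting. It does not support a claim that the stated power is materially missed. A larger effect requires a lag in the eligibility extract, which the documents neither state nor quantify. Severity: minor, worth correcting because the correction is so cheap.

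**What to change.** 1. In the weekly code, require no antidepressant fill and no psychotherapy visit from the eligible diagnosis through the day of randomisation, checked in the same way for every patient before assignment.
2. In section 12.4, define the event as the first fill or visit since the eligible diagnosis, dated within 60 days after randomisation. Judge it by service date on the final extract, identically in both arms, and keep all assigned patients in the denominator so that intention-to-treat is unchanged. Because it works on service dates, this rule also stops late-arriving records from being scored as initiation, whatever the lag.
3. Report by arm how many patients had a fill or visit dated between diagnosis and randomisation. This shows whether the problem is nearer 1% or larger.

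The cost is a date limit in the code, one sentence in section 12.4 and one line in the results. No new data are needed, because sections 23.3 and 33.5 already list diagnosis, visit and fill dates in the shared data set. Reported initiation rates may be slightly lower.

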#### **Pilot Trial Design**

Each week, the computable EHR phenotype described above will be used to identify patients meeting criteria for failure to initiate depression treatment during the prior week. All eligible participants will be randomly assigned either to continued usual care (i.e. no contact from study staff) or to an outreach intervention described above. Engagement in care and recorded clinical outcomes over the subsequent 60 days will be assessed using health system records.

**Intervention Assignment** - All eligible patients will be randomly assigned (1:1 ratio) to either continued usual care or attempted outreach using a masked table of computer-generated random assignments. Randomization will be stratified by study site and use a permuted block design, with randomly varying block sizes of 4, 6, 8, 10 and 12.

**12.3 \* Provide a brief description about the quality management plan for the selection of study participants and integrity of the data. Specify the verification or audit process to ensure data and/or participants meet the study inclusion criteria. Additionally, describe the mechanism to ensure that study data is well secured and accurately entered. (e.g. two staff verification process to ensure entry criteria are met prior to using data or including a participant; safety reports; Data Safety Monitoring Board and/or screening checklists.)**

- All staff will be training in HIPAA privacy rules, human subjects protections, authorization of access by CIHR/HFHS IT, password protection, encryption, physical security, and separation of identifiers from data
- We plan to archive the deidentified data at the end of the study for the federally-mandated retention period or at least seven years, whichever is later.
- A Data Use Agreement will be executed between all sites prior to the transfer of any data. Data exchanged between the sites will contain the minimal information necessary and will be in the form of a limited data set.
- Data will be stored on password-protected encrypted devices and servers.

No identifying information will be linked to the audio-recordings of the focus groups interviews. Participants will not be asked to state their name for voice linking. Audio-recordings will be sent to a professional transcriptionist via secured transfer. Once the transcription is received the audio-file will be permanently destroyed. All data will be transferred from an encrypted computer, which is password protected, to a secured server during data collection. Identifiers will be removed from all data obtained in this study and identifiers will be destroyed following the completion of the study, prior to closure of the IRB protocol.

We will convene a Data and Safety Monitoring Board including:

- A clinician with expertise regarding psychotherapy for depression ([name], VA Pacific Islands Health Care Division)
- A clinician with expertise regarding medication treatment for clinician ([name], Harvard University)
- A statistician with expertise regarding effectiveness or pragmatic trials ([name], National Center for PTSD, Palo Alto)

DSMB members will not be affiliated with research centers or health systems participating in this study.

The DSMB will meet three times during the pilot trial portion of the project:

- One meeting prior to beginning enrollment to review all study procedures

- One meeting when approximately half of the planned sample has been enrolled to review enrollment progress, quality/fidelity of intervention delivery, and any adverse events identified by or reported to study staff
- One meeting when the full sample has been enrolled to review enrollment progress, quality/fidelity of intervention delivery, any adverse events identified by or reported to study staff, and quality/integrity of outcome data

The DSMB will have authority to:

- Require changes to study procedures
- Terminate enrollment because of inadequate progress
- Terminate delivery of interventions because of concern regarding effective or safe delivery

Given the sample size, the relatively short recruitment period, and the delay in availability of outcome data extracted from health system records; we do not propose any interim analyses of study outcomes. Interim analyses prior to completion of enrollment would not have adequate power to detect either significant benefit or significant harm from the outreach intervention

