Based on previous experience, we expect that most telephone outreach would involve leaving telephone message reminders regarding patient portal messages rather than live contact with participants. We have developed a phone script (see document Phone\_Script\_Outreach). For participants with PHQ-9 score  $\geq 15$  or response to item 9  $\geq 2$ , initial contact will be by telephone. For participants with PHQ-9 score less than 15 and a response  $< 2$  to PHQ-9 item 9, initial contact will be by online message. Using motivational interviewing scripts and tools developed in previous research programs, outreach clinicians will assess readiness and respond with appropriate tailored interventions focused on either motivational enhancement or action planning. Depending on clinical need, outreach clinicians will also assess risk of self-harm, initiate safety planning, and facilitate urgent mental health care (Safety Protocol document).

Monitoring initiation and adherence – Based on experience in the MHRN Suicide Prevention Outreach Trial and Automated Outreach project, outreach clinicians will track reading outreach messages as well as initiation of and early adherence to depression treatment (either medication or psychotherapy) using EHR-based population management tools (Epic Registry and Reporting Workbench functionality).

Outreach clinicians – Outreach clinicians will be either registered nurses or masters-prepared mental health clinicians. Following a typical model for implementation of collaborative care or care management programs, outreach clinicians will receive approximately 8 hours of initial training and will participate in bi-weekly supervision teleconferences during the period of active intervention delivery.

Identification of Study Participants (Phases I and II):

The following criteria will be used to guide identification of participants for the formative evaluation (Phase II focus groups) as well as a clinical trial (Phase III). \*However, during the Phase II we will also invite participants who have initiated treatment following a new depression diagnosis to ensure this perspective is also represented in the focus groups.

Using a computable EHR phenotype developed and validated in MHRN research, these data warehouses (e.g., VDW, Clarity) at each site will be used to identify adult patients meeting the following criteria:

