Provider Survey: Providers will be recruited digitally to complete a brief 10-minute survey (Provider Recruitment Email.doc). We will work with clinical liaisons within each health system to recruit eligible providers. Invitations to providers will either be sent by the Site-PI or a designated clinical partner (e.g., [name] at KPHI). The survey invitation will contain an informational sheet (Provider\_Information\_Sheet.doc) that will be attached to the electronic message and attached as an attachment.

Phase III:

Once a participant is determined to be eligible for the study using the algorithm described in previous sections, the participant will be randomized to either standard care or outreach messaging groups. Participants randomized to standard care will not be contacted by the project team. Follow-up data will be collected (see previous section) regarding treatment initiation and depression remission (follow-up PHQ-9 scores) for 60 days after randomization for standard care participants. Participants randomized to the outreach group will receive either an initial phone call or secure message from the study team. For participants with PHQ-9 score less than 15 and a response <2 to PHQ-9 item 9, initial contact will be by online message. For participants with PHQ-9 score ≥15 or response to item 9 ≥2, initial contact will be by telephone. Up to four outreach attempts will be made per participant. If initial outreach occurs by secure message and it is not read within three days of sending, up to three telephone outreach attempts. Telephone outreach will take two times in one week, and then two weeks following the last attempt.

We propose a waiver of the usual requirement for informed consent to identify potential participants and assign patients to either continued usual care or attempted outreach. We believe that this approach (waiver of consent in such a modified Zelen or randomized encouragement design to evaluate a low-risk outreach intervention) satisfies regulatory requirements and ethical standards for waiver of consent. Use of this approach in similar previous MHRN trials has been vetted with the DHHS Office for Human Research Protections and approved by MHRN health system institutional review boards.

For participants assigned to outreach, the initial outreach message will include abbreviated informed consent information, including (see outreach message consent document):

- Description of the outreach program

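### The only adverse-event source stated for the DSMB depends on study staff, who contact only the outreach arm, so harm cannot be compared between arms

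*Combined protocol and SAP*

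**What the plan says.** **Safety input.** Section 12.3 schedules three DSMB meetings. At half and at full enrolment the safety item is "any adverse events identified by or reported to study staff". No event list, capture method or split by arm is given. Among the board's powers is: "Terminate delivery of interventions because of concern regarding effective or safe delivery".

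**Contact by arm.** Usual care is "continued usual care (i.e. no contact from study staff" (12.2, Pilot Trial Design). Section 22.1 repeats it: "Participants randomized to standard care will not be contacted by the project team". For outreach, 22.1 states: "Up to four outreach attempts will be made per participant". Section 12.2 (Phase III) adds that, depending on clinical need, "outreach clinicians will also assess risk of self-harm, initiate safety planning, and facilitate urgent mental health care". Patients with a higher PHQ-9 total or item 9 score are approached first by telephone.

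**Records.** For both arms, "Engagement in care and recorded clinical outcomes over the subsequent 60 days will be assessed using health system records" (12.2). The outcomes named are treatment initiation and PHQ-9 response or remission (12.4, 22.1). The limited data set is described by example only, as dates of diagnosis, psychotherapy and prescription fill (33.5). Chart review is described as support for outreach clinicians and a check on the selection algorithm (12.2).

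**Interim analysis.** Section 12.3 proposes none, citing sample size, the short recruitment period, delay in outcome data and inadequate power for benefit or harm.

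**The concern.** These are patients with a PHQ-9 of at least 10 and no treatment 30 days after diagnosis. Some psychiatric events can be expected in both arms whatever outreach does. If such events become known mainly through contact with study staff, and one arm has no such contact, the counts measure the intensity of observation as well as harm.

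The consent design widens the gap. Assignment is made under a waiver, and only the outreach message carries study information (22.1). Usual-care patients therefore have no evident reason or route to report an event to the study.

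Two errors are possible. Background events in the outreach arm could be read as caused by outreach, and the board has the power to stop delivery. Conversely, a real excess could be dismissed as the product of closer observation. The planned full-scale trial would also inherit no usable background rate.

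**Working it through.** **1. The plan's own figure.** No safety rate or safety power is stated. The nearest figure is the primary-outcome power in 12.4: 10% against 22%, 200 per group, two-sided 5%, 90%. The normal approximation used is

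power = Φ{ [d√n − 1.96√(2p̄(1−p̄))] / √(p₁(1−p₁) + p₂(1−p₂)) }.

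With d = 0.12 and p̄ = 0.16: (14.142 × 0.12 − 1.96 × 0.5185) / 0.5115 = 1.331, and Φ(1.331) = 0.908. The 90% reproduces, so the same formula is used in step 4.

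**2. What feeds a safety count in each arm, as written.**

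| | Outreach | Usual care |
|---|---|---|
| Staff contact | up to four attempts | none |
| Self-harm risk assessment by study clinicians | yes, by clinical need | none described |
| Told of the study | in the initial outreach message | no notice described |
| Records read for 60 days | yes | yes |
| Harm outcome defined in those records | none | none |

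The only row that is equal and informative is the record reading, and no harm item is attached to it.

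**3. How large the skew could be.** Let r be the true 60-day event rate, equal in both arms, and let c₁ and c₀ be the fractions of events that reach the DSMB from outreach and usual care. With n = 200 per arm, the expected spurious difference in counts is n·r·(c₁ − c₀). The documents give none of r, c₁ or c₀. The values below are assumptions, and c₀ = 0 is the limiting case, not something the plan states.

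| r | true events per arm | count seen, c₁ = 1, c₀ = 0 | count seen, c₁ = 0.5, c₀ = 0 |
|---|---|---|---|
| 1% | 2 | 2 v 0 | 1 v 0 |
| 2% | 4 | 4 v 0 | 2 v 0 |
| 5% | 10 | 10 v 0 | 5 v 0 |

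As a yardstick, 6 v 0 in 200 per arm gives a Fisher exact p of 0.030, and 5 v 0 gives 0.061. With no true difference, the chance of 6 or more outreach events is the upper tail of a Binomial(200, r·c₁). At r = 1%, 2% and 5% it is 1.6%, 21% and 94% with c₁ = 1, and 0.1%, 1.6% and 38% with c₁ = 0.5. At low rates and partial capture a nominally significant false signal is unlikely, but the counts still cannot be compared.

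**4. What symmetric capture would achieve.** With complete records in both arms and the step 1 formula:

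- Doubling from 1% to 2%, 200 per arm: (14.142 × 0.01 − 1.96 × 0.1719) / 0.1718 = −1.138, power 13%.
- Doubling from 2% to 4%, 200 per arm: (14.142 × 0.02 − 1.96 × 0.2412) / 0.2408 = −0.789, power 22%.
- Fisher's exact test gives 4% and 13% for the same two cases.
- At half enrolment, about 100 per arm, the approximate figures are 8% and 13%.
- The 95% interval half-width at equal rates, 1.96√(2r(1−r)/200), is 2.0 points at 1%, 2.7 at 2% and 4.3 at 5%.

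**The case against.** A reader might infer that usual-care events are wholly invisible to the study. The documents do not support that. The wording covers events identified by staff as well as those reported to them, and identification could include what staff see in records, which are read for both arms. A safety protocol and a crisis tracking database are listed (12.2, 15.2) but not reproduced, and could contain a two-arm procedure. What stands is that none of the text available provides for one. If those documents do, 12.3 should say so.

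A reader might also infer that the DSMB cannot judge whether outreach is safe. That is too strong. The board can examine individual outreach-arm events and fidelity of delivery, can stop delivery, and can require procedural changes, including asking for a two-arm listing at its first meeting. What it lacks is a comparable control rate.

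Capture in the outreach arm will also be partial, because 12.2 expects most telephone outreach to end in messages rather than live contact. This narrows the skew without removing it.

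The strongest objection is the plan's own: outcome data arrive late and power for harm is poor. Step 4 confirms the second part. Both facts argue against a test or a stopping rule. Neither is a reason to gather events differently in the two arms, or to omit a listing once follow-up is complete. The application's position that outreach is low risk bears on how much safety data to collect, not on whether collection should be equal.

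**Conclusion.** The point holds in a limited form. The only adverse-event source stated for the DSMB runs through study staff, staff contact only the outreach arm, and no records-based harm outcome is defined in the text available. Counts gathered this way will be skewed towards outreach and will not support a between-arm comparison of harm.

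The size of the skew cannot be fixed from the documents. In the limiting case of no usual-care capture, at assumed rates of 1-2%, it is a spurious excess of 1-4 events per 200, depending on whether half or all outreach events are captured. The conclusion that the arms are not comparable needs only unequal capture, not any particular rate. It would fall away if the unseen safety documents already specify equal capture from records. The primary analysis is unaffected, because its outcome comes from records in both arms.

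**What to change.** In 12.3, add a short harm list drawn from health records, for example death, coded self-harm, and psychiatric emergency visit or admission. Use the same codes and the same 60 days after randomisation in both arms.

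- Give it to the DSMB by arm as a descriptive listing with confidence intervals, with no test and no stopping rule attached.
- Present the data available at the half-enrolled and fully-enrolled meetings, marked as incomplete. Complete the listing once the last participant's 60-day window and the record lag have passed.
- List staff-identified events separately, as outreach-only, and do not compare them between arms.
- If the safety protocol or crisis tracking database already covers part of this, cite it in 12.3.

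**Cost.** One added query on data warehouses already in use, and one table. An IRB and data-agreement modification is likely, because usual-care data are used under waivers, the application declares its PHI to be the minimum necessary (30.6), and 36.1 limits use to what the application describes. Listings will be incomplete at both enrolment-based meetings, since the most recent enrollees will not have reached 60 days. Power for rare harms stays low, about 13-22% for a doubling from an assumed 1-2% with 200 per arm. The gain is a fair comparison and a background rate for the full-scale trial, not a sensitive test.
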